## METHOD

The study will include forty two neonates ( $n=42$ ) born  $\leq 34$  weeks of gestational age. Four bottle-feeding sessions will be tested in each of the newborn: two in the SEP and two in the SLP. The position for the first study will be randomly assigned, then positioning will be changed after each feeding session. In one day, only two consecutive feeding sessions which will be included to the study in order to minimize fatigability as a disrupting factor. The levels of saturation ( $SpO_2$ ) and heart rate (HR) will be measured as the parameters indicative of the newborn's physiological stability. The factors determining the qualitative aspects of feeding included the total time of declines of  $SpO_2 \leq 85\%$ , level of the newborn's alertness according to the Neonatal Behavioral Assessment Scale (NBAS), and the occurrence of choking episodes. The proportion of milk consumed (volume of milk eaten relative to the expected volume) and the duration of the feeding and feeding session will be also recorded.

Each feeding session will be recorded with a video camera. It should be mentioned that participation in the study will not oblige the parents to use any of the positions which will be used during the study and to bottle-feeding. Bottle-feeding will be continued with attempts of the breastfeeding, if only it will be possible.

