## INCLUSION CRITERIA

- circulatory and respiratory stability;
- readiness for oral feeding according to each child's Speech-Language Pathologist assessment;
- prematurely born infants who were in the process of being transferred from enteral nutrition (or enteral nutrition + parenteral nutrition) to full

- oral feeding and were fed orally at least 4- 6 times within twenty-four hours;
- parents gave informed consent to participate their infant in the study.

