## DETAILS OF POSITIONING IN SLP AND SEP POSITIONS

SLP: Infant placed in a SLP on the researcher's lap. Head of the infant symmetrically placed between the shoulders, supported by the researcher's. Shoulder girdle higher than pelvic girdle, head and back in a straight line – a slight natural bent of the body is allowed. Legs bend at an angle of approx. 90° in the natural flexion of the knee and ankle joint. The infant's arms close to the midline (on the bottle of researcher's hands).

SEP: Infant placed in a SLP on the researcher's lap. The head rests on the researcher's hand. Shoulder girdle higher than pelvic girdle, head and back in a straight line at an angle of 40-45° to the ground – a slight natural bend of the body is allowed. Legs bend at an angle of approx. 90° in the natural flexion of the knee and ankle joint. The infant's arms close to the midline (on the bottle of researcher's hands).

The research is approved by the Bioethical Commission of the Polish Mother's Memorial Hospital Research Institute, Łódź, Poland - opinion no. 95/2016.

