## STUDY DESIGN

The study is designed as a crossover study - alternate study. It will be a randomized trial. Each infant will be bottle-fed four times: twice in the SEP and twice in the SLP. In each of the study positions 84 feeding sessions will be analyzed (total amount of feeding sessions which will be analyzed will be 168). The position for the first trial will be randomly assigned (random table), then positioning will be changed after each feeding session. The study will include observation of the newborn before, during and after the feeding and the following measurements:

- A. 2 minutes before the feeding session: oxygen saturation ( $SpO_2$ ) level, heart rate (HR) (pulse oximeter data), alertness level
- B. 3rd minute of the feeding session:  $SpO_2$ , HR, alertness level
- C. 10th minute of the feeding session:  $SpO_2$ , HR, alertness level, volume of food eaten
- D. the end of the feeding session:  $SpO_2$ , HR, alertness level, volume of food eaten
- E. 10 minutes after the feeding session:  $SpO_2$ , HR, alertness level

The declines of  $SpO_2 \leq 85\%$  level, total time of feeding and feeding session, occurrence chocking episodes also will be recorded.

During the study feeding, normal feeding session procedures will be applied: avoidance of excessive stimuli by ensuring calm environment with limited level of light and noise, pauses in the feeding after a series of suckling (interval feeding), manual support within the articulation apparatus to improve lip tightness and/or mandibular function. Stimulation of the suction reflex will be also allowed.

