# Statistical Analysis Plan

In order to verify hypothesis stated in this research, statistical analysis will be conducted using IBM SPSS v. 25 and Jamovi v1.2.8. Frequency distribution analysis, basic descriptive statistics with Shapiro-Wilk's test for normality of distributions, *t*-tests for independent samples, two-way independent mixed ANOVAs as well as chi-squared tests of independency will be computed.

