## WHAT WILL BE ANALYZED?

- Differences in changes in blood oxygen saturation due to the position of the baby during feeding
- Heart rate variations due to the position of the baby during feeding
- Differences in the change in baby's activity due to the baby's position during feeding
- The position of the baby during feeding and choking episodes
- Differences in the proportion of the volume of eaten food due to the position of the child during feeding
- Differences in feeding times and feeding sessions due to the position of the baby during feeding
- Differences in the time of saturation decrease to the level of  $\leq 85\%$  due to the position of the child during feeding

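### Independent-sample tests leave between-infant variance in the error term of a crossover and the pre-feed value A has no defined role; a within-infant model recovers most of the lost precision, A as covariate a little more

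*Combined protocol and SAP*

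**What the plan says.** Under STUDY DESIGN, 42 infants are each fed four times, twice semi-elevated and twice side-lying. The starting position is random, and "then positioning will be changed after each feeding session". METHOD adds: "In one day, only two consecutive feeding sessions which will be included to the study". SpO2, heart rate and alertness are read at five points per session. Point A is "2 minutes before the feeding session: oxygen saturation" and the other two measures. B is the third minute, C the tenth minute, D the end of the session, and E ten minutes afterwards.

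The Statistical Analysis Plan section lists t-tests for independent samples and says that "two-way independent mixed ANOVAs as well as chi-squared tests of independency will be computed". It names no ANOVA factors, covariate, infant term or definition of change. The list of analyses asks for "Differences in changes in blood oxygen saturation due to the position of the baby during feeding", with similar wording for heart rate and activity, but gives no reference time. It also lists outcomes without a pre-feed value, such as "The position of the baby during feeding and choking episodes".

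The positioning section describes the hold ("Infant placed in a SLP on the researcher's lap") but not when the infant is placed in it relative to A.

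**The concern.** A crossover is chosen so that each infant serves as its own control. A test for independent samples gives that up: the spread between infants cancels from the position difference but stays in its estimated standard error. The sample is fixed at 42, so precision lost in this way cannot be bought back.

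The undefined role of A is a second, smaller matter. A could be one of five time levels, a value to subtract, a covariate, or left out. These choices differ in power, and leaving them open allows the choice to be made after the data are seen. At stake is the chance of detecting a modest position effect on the three outcomes that have an A value.

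**Working it through.** **Plan's own figure.** 42 × 2 = 84 sessions per position and 42 × 4 = 168 in total, as STUDY DESIGN states. There is no power calculation to reproduce.

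**Inputs.** From the documents: 42 infants, two sessions per position, points A–E. Assumed: two-sided 5% level; a single reading has variance 1, split into infant (u), session (s) and residual (r); the session part is correlated ρ^|i−j| between points, with ρ = 1, 0.8 or 0.6; 0.25 SD effect at B, C and D; the effect is the same in every infant.

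**Formulas for the B–D average.**
- Within-infant variance: V = r/3 + s(3 + 4ρ + 2ρ²)/9
- Covariance with A: c = s(ρ + ρ² + ρ³)/3
- SE, sessions independent (nominal): √((u + V)/42)
- SE, within infant: √(V/42)
- SE, A as covariate: √((V − c²/(s + r))/42)

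Power of the independent test uses its nominal SE for the critical value (1.974 × SE) and the within-infant SE as the true sampling error. The other two use noncentral F with (1,122) and (1,121) df.

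**Results at u/s/r = 0.3/0.2/0.5.**

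| | ρ = 1 | ρ = 0.8 | ρ = 0.6 |
|---|---|---|---|
| V | 0.3667 | 0.3329 | 0.3027 |
| c | 0.2000 | 0.1301 | 0.0784 |
| SE, independent | 0.1260 | 0.1228 | 0.1198 |
| SE, within infant | 0.0934 | 0.0890 | 0.0849 |
| SE, with covariate | 0.0858 | 0.0857 | 0.0836 |
| Power, independent | 51% | 53% | 56% |
| Power, within infant | 76% | 80% | 83% |
| Power, with covariate | 82% | 82% | 84% |

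For ρ = 1: √((0.3 + 0.3667)/42) = 0.1260 and √(0.3667/42) = 0.0934. The infant term cuts the nominal variance by u/(u + V) = 45.0; 47.4; 49.8%. The covariate cuts the within-infant variance by a further 15.6; 7.3; 2.9%, worth 6.8; 2.9; 1.1 power points.

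**Direction of the error.** Without a position effect, the independent test at ρ = 1 rejects with probability 2(1 − Φ(1.974 × 0.1260/0.0934)) = 0.8%. It is conservative, not liberal.

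**Range over shares (ρ = 1).**
- 0.1/0.2/0.7: V = 0.4333; SE √(0.5333/42) = 0.1127 against √(0.4333/42) = 0.1016; power 60.7% against 68.5%.
- 0.5/0.2/0.3: V = 0.3; SE √(0.8/42) = 0.1380 against √(0.3/42) = 0.0845; power 39.5% against 83.5%.
- Covariate's own variance cut at ρ = 1; 0.8; 0.6: 29.7; 14.2; 5.9% at 0.3/0.3/0.4, and 4.8; 2.1; 0.8% at 0.3/0.1/0.6. It is zero with no session variance.

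**If the position × time interaction is tested instead.** A constant infant level cancels from this test, so the independence problem does not reach it. Its cost comes from using A as a level. At 0.3/0.2/0.5 with the same flat effect, 4-df power is 48.8; 43.0; 39.4% with A as a level. A within-infant test of B–E without A has 61.4; 61.6; 64.1%, and with A as covariate 66.8; 64.8; 65.5%.

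**What adjustment can cost (0.3/0.2/0.5).** The slope on A is b = c/(s + r) = 0.286; 0.186; 0.112.
- *Position already shifts A by 0.25 SD.* The adjusted estimate of a true 0.25 SD effect is 0.25(1 − b) = 0.179; 0.204; 0.222, with power 54; 65; 75% against 76; 80; 83% unadjusted.
- *Carryover from the day's first feed, in one direction only, moves A by 0.25 SD and nothing else.* Half the infants are affected, so A is unbalanced by 0.125. Adjusted bias is 0.125b = 0.036; 0.023; 0.014 SD, with type I error 7.0; 5.8; 5.3%. The unadjusted estimate is unbiased.
- *The same shift persists into B–D, fading at rate ρ.* Unadjusted bias is 0.125; 0.081; 0.049 SD (type I error 26; 15; 9%). Adjusted bias is 0.089; 0.058; 0.035 SD (18; 10; 7%).

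**The case against.** Leaving out a covariate is not an error, and no document gives a correlation between A and later readings. A precedes the feed, and enrolled infants must show "circulatory and respiratory stability", so the fading patterns are plausible and the covariate then adds only 1 to 3 points. That stands, and it is why the covariate comes second here.

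The word mixed might be meant to cover repeated readings. It may well cover the five time points, but no infant factor is named, and the t-tests are explicitly for independent samples. The request for differences in changes does point towards the position × time test, which does not suffer from between-infant variance. That limits the concern to comparisons of level: t-tests and position main effects.

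A reader might infer that power is as low as 15–17%, the figure for a position main effect averaged over A–E. The plan never says that this effect will be read, and its wording points elsewhere. A reader might also infer that reusing infants produces false positives. Under the stated assumptions the opposite holds, because each infant contributes equally to both positions.

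Nor does leaving A out make the estimate safe. It is unbiased only if carryover touches A alone; if carryover persists into the feed, the unadjusted estimate is the more biased of the two.

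**Conclusion.** The concern holds in two parts of unequal size. For comparisons of level in SpO2, heart rate and alertness, independent-sample tests waste the crossover's main advantage: at 0.3/0.2/0.5, power is 51–56% where a within-infant analysis has 76–83%. The loss shrinks as infants become more alike. A as a covariate is an optional extra worth 1 to 7 points at these shares, possibly nothing, and harmful if the infant is already in the study position at A.

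This is lost efficiency and an unspecified choice, not an error shown to reverse a result. All sizes are illustrative. They rest on assumed variances, normal readings, equally spaced points (D has no fixed time) and a common position effect. They are less reliable for SpO2, which is capped at 100%, and do not carry over directly to alertness, which is an ordered level. The covariate question does not arise for choking, share of volume taken, durations or time at or below 85%, which have no A value.

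**What to change.** - For SpO2 and heart rate, replace the independent ANOVA with a mixed model of B, C, D and E. Random effects: infant, and session within infant. Fixed effects: position, time, position × time and session order. Use an ordinal counterpart for alertness.
- Prespecify one position contrast, for example the B–D average.
- Name the within-infant estimate without A as primary.
- State whether A is read before the infant is placed in the study position. Only if so, run a prespecified secondary analysis adding the session's A and the infant's mean A.
- Report mean A by position and session, so that a position or carryover effect on A can be seen.

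Cost: wording, and one or two degrees of freedom for the secondary analysis. No new infants, sessions or measurements. The remaining risks are the two quantified above: adjustment removes part of the effect if position already affects A, and carryover can bias either estimate. A session-order main effect does not remove the carryover bias. If only part is adopted, the within-infant model without A as a level matters more than the covariate.

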## WHAT WILL BE ANALYZED?

- Differences in changes in blood oxygen saturation due to the position of the baby during feeding
- Heart rate variations due to the position of the baby during feeding
- Differences in the change in baby's activity due to the baby's position during feeding
- The position of the baby during feeding and choking episodes
- Differences in the proportion of the volume of eaten food due to the position of the child during feeding
- Differences in feeding times and feeding sessions due to the position of the baby during feeding
- Differences in the time of saturation decrease to the level of  $\leq 85\%$  due to the position of the child during feeding

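### Total time at SpO2 of 85% or less is compared between positions with no denominator, so on its own it cannot separate a higher desaturation rate from a longer feed

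*Combined protocol and SAP*

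**What the plan says.** - **Measure.** The protocol's METHOD section states: "The factors determining the qualitative aspects of feeding included the total time of declines of" SpO2 to 85% or less. This is a cumulative time, and no divisor is given.
- **Comparison.** The SAP list under WHAT WILL BE ANALYZED? has "Differences in the time of saturation decrease to the level of" 85% or less, by position. No rate, share of session, offset or duration covariate appears there or among the SAP's named methods.
- **Duration as an outcome.** The same list includes "Differences in feeding times and feeding sessions due to the position of the baby during feeding".
- **Recording.** STUDY DESIGN records the "total time of feeding and feeding session", so a denominator will exist for every session.
- **Session length.** It is not fixed. One measurement point is simply "the end of the feeding session", and no maximum is stated.
- **Test.** The SAP names t-tests for independent samples, mixed ANOVAs and chi-squared tests without assigning them to outcomes. The t-test is the natural reading for a continuous quantity compared between two positions, and I take it as the planned test here.

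Milk intake, by contrast, is expressed relative to the expected volume. Desaturation time has no such step, and nothing says how it is to be read together with duration.

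**The concern.** Time below a threshold accumulates with time observed. If one position gives longer feeds, its infants have more minutes in which to desaturate. If its feeds end sooner, they have fewer. A difference in total seconds can therefore come from the rate of desaturation, from the length of the feed, or from both.

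These explanations mean different things to someone choosing a position. The introduction treats falls in saturation as an unfavourable factor and a cause or symptom of stress, so a difference in this outcome is likely to be read as one position being safer. As written, the SAP gives no way to say whether the infant desaturates more readily in that position or is simply fed for longer. If the choice of denominator is left until the data are seen, two measures that may disagree will both be available.

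**Working it through.** **The plan's own figures.** 42 infants × 2 sessions per position = 84 per position, and 42 × 4 = 168 in total. Both match STUDY DESIGN. The documents give no alpha, power, expected desaturation time or expected session length, so every rate and duration below is an assumption.

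**Arithmetic.** For each session,

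seconds at 85% or less = share of session at 85% or less × session seconds.

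At an equal share, the ratio of total times equals the ratio of durations. With an assumed 5% share:

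- 20 min: 0.05 × 1200 = 60 s
- 22 min: 0.05 × 1320 = 66 s
- 24 min: 0.05 × 1440 = 72 s
- 30 min: 0.05 × 1800 = 90 s

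The same 90 s against 60 s also arises with no difference in duration, if the share is 7.5% rather than 5% in 20-minute sessions (0.075 × 1200 = 90). Total time alone cannot tell these two cases apart.

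**Simulation at an equal per-minute rate.** 42 infants, two sessions per position, 4,000 trials per setting, two-sided 5% tests. Assumed: mean session 20 min in the shorter position, log-SD of duration 0.2, 0.1 to 0.4 episodes per minute, mean episode 10 s, gamma between-infant variance 0.5. Entries are the percentage of trials with a significant difference.

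| Longer feeds by | Total time, independent t | Total time, paired t |
|---|---|---|
| 0% | 0.2 to 1.7 | about 5 |
| 10% | 2 to 4 | 9 to 18 |
| 20% | 11 to 16 | 21 to 56 |
| 30% | 25 to 47 | 38 to 87 |
| 50% | 63 to 95 | 77 to near 100 |

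Dividing each session's time by its length gives 4.2% to 5.7% (paired) and 0% to 2.0% (independent) at every duration ratio. Further runs at 25% longer, with rates up to 0.4 per minute, gave 20% to 30% for the independent t-test and 40% to 74% paired. For rates of 0.15 to 0.4 per minute the independent t-test at 50% longer gives 75% to 95%; the 63% in the table belongs to the lowest rate, 0.1.

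The independent t-test falls below 5% at equal durations because it ignores that each infant is fed in both positions. That is a separate matter, but it is why its figures are lower than the paired ones.

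**The opposite assumption.** Suppose the number of episodes per feed is the same however long the feed lasts, for example because they cluster early. With 60 s in each position and sessions of 20 and 25 min, the shares are 60/1200 = 5% and 60/1500 = 4%, so the longer-feeding position looks better with identical desaturation. Simulated with a mean of 3 or 8 episodes of 12 s, gamma shape 2, log-SD 0.2 and 2,000 trials, paired rejection at 25% longer is about 5% for total time and 35% to 68% for percentage. At 50% longer it is about 5% against 81% to 99%.

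Neither measure is neutral to duration under both assumptions, and the documents do not say which assumption is nearer the truth.

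**The case against.** The best defence is that total time per feed is a legitimate quantity. If a position lengthens feeds and the infant spends more seconds desaturated as a result, that is a real effect of position. **This stands.** A reader might take the rejection rates above as false-positive rates, but the null hypothesis for total time is false whenever durations differ at an equal rate, so they are power to detect a real difference in burden.

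Second, METHOD names SpO2 and heart rate levels as the indicators of physiological stability and places desaturation time among the qualitative aspects of feeding. The levels are taken partly at the 3rd and 10th minute, which match on elapsed time and do not accumulate. **This also stands.** A reader might infer that the trial's judgement of stability rests on an unadjusted total. The documents do not say so.

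Third, a percentage has the mirror-image weakness, because its denominator is itself an outcome of position. **This stands too**, and rules out percentage as the sole deciding measure.

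Fourth, duration is reported by position anyway, so a reader can see whether the two move together. **This stands only in part.** Two separate group comparisons do not give the per-session share or its within-infant difference, and no interval would be attached to it.

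Finally, the documents list duration as a comparison. They do not predict that it will differ, and they do not mention abandoned feeds. The problem is conditional on a difference that may not occur.

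**Conclusion.** The point holds as a gap in what the planned comparison can show. Total time at 85% or less is a sound measure of burden per feed, but alone it does not say whether a difference between positions reflects rate, duration or both. Duration is an outcome the plan itself compares, and both components are recorded.

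The practical size depends on how far durations differ, which the documents do not indicate. Under the assumed equal rates it is negligible at 10% longer feeds with the independent t-test, moderate at 25% and large at 50%. A paired analysis, which suits the crossover, would pick up the duration-driven difference more often.

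The stronger reading, that comparing total time is an error and should give way to percentage, is not supported. It needs a constant per-minute rate, which no part of the documents establishes. This is a worthwhile addition to make before analysis. It does not invalidate the trial.

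**What to change.** In the SAP, under WHAT WILL BE ANALYZED?:

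1. Keep total time at SpO2 of 85% or less.
2. Add, as a pre-specified companion, the percentage of session time at 85% or less: seconds at 85% or less divided by session seconds.
3. State one window for both numerator and denominator. The documents do not say whether declines are timed over feeding, the whole session, or also the 10 minutes afterwards.
4. Analyse both measures within infant, and report each estimated difference with a confidence interval beside the difference in session duration.
5. State that the three will be interpreted together.

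Percentage should not be made the only deciding measure. The SAP should also not say that a difference in total time is due to session length whenever percentage shows no significant difference, since a non-significant result does not show that the rates are equal.

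The cost is one derived variable and a few SAP sentences, with no new measurements or infants. There is one more estimate to report; it is noisier in very short sessions, and its denominator is itself affected by position.
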